Primary Outcomes. Two primary outcomes will be assessed at the level of the participant: the probability of receiving at least one 1) test and 2) vaccination dose within 3 months of baseline. Outcomes will be ascertained specifically by testing/vaccine registry data held by city and state held vaccine registries (Letters, [name], [name], [name]). Study participants will sign release of information forms, as in RADx-UP Phase I, in order for study staff to obtain 3-month testing/vaccination disposition statuses. Covid testing/vaccination status may also be provided by subject showing a copy of their covid testing result and/or vaccination information. This may be provided in person, shown during a video call, emailed or texted as a picture. Finally, study staff will reach out to all study participants (N=800) at 3 months following baseline to collect information on testing and vaccination uptake among study participants and barriers and facilitators for both network members and study participants. During

this assessment, information on situation appropriate testing will be collected to better understand the circumstances and context of testing. At the time of this writing, situation appropriate testing includes testing if symptomatic, if exposed to someone with COVID-19 infection and if entering a congregate living setting. Only participants reporting symptoms, exposure, and/or congregate housing will be included in the primary testing outcome analysis; post-hoc analysis will include all participants tested irrespective of the situation/context.

Secondary Outcome. Two secondary outcomes will be assessed at the level of the secondary subjects (network member connected to primary participant): the probability of receiving at least one 1) test and 2) vaccination dose within 3 months of baseline. Network member information, including identifying information will be collected during the baseline assessment through specialized network canvas software (described above). The secondary outcome will be determined based upon self-report from participants during the 30 and 90-day follow-up surveys. Note that this information is collected based asking the study subject whether the social network contact underwent these activities and not from contact with or medical record data collection of the social network member. Analyses for our secondary outcome will account for variability in network size across individuals.

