Primary and Secondary Outcome Analysis. Two sets of analyses will be performed. The first will focus on testing and vaccination among participants and the second will focus on testing and vaccination among the networks of participants. Testing and vaccination will be analyzed as separate outcomes throughout. The primary outcome analysis will compare the probability of testing and the probability of vaccination among participants assigned to Educational vs. Motivational intervention. Secondary analyses will compare the total number of network members tested and vaccinated and the probability of testing/ vaccination among network members of participants assigned to Educational vs. Motivational intervention (Aim 1). All analyses will use generalized linear models with link functions based on the distribution of the outcome (logistic or log binomial for binary outcomes; negative binomial regression for count outcomes) and random effects as appropriate to account for clustering of network members within participants. The initial analysis will include an indicator for intervention assignment as the only independent variable and will not adjust for covariates since the randomization should ensure comparability between the groups on measured and unmeasured confounders, though group characteristics at baseline will be inspected visually for imbalances (Aim 1a). We will then incorporate participant (e.g., mental health, early adopter status) and network level (e.g., network thresholds, density) covariates to improve the precision of the estimates and to identify sociodemographic and network characteristics associated with differences in testing and vaccination yield. In addition, we will explore interactions between intervention group (Education vs. Motivational intervention) and participant characteristics to determine whether the intervention is more effective in certain groups than

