others (Aim 1b). Because we will likely have limited power to detect small to medium sized interaction effects in subgroup analyses, we will consider these analyses exploratory, with the goal of generating insights to guide future work. Partial pooling within a Bayesian estimation framework⁷¹ will be used to avoid bias and address the issue of multiple comparisons when testing interactions. We will also include an indicator for time trends to control for potential changes in testing recommendations, vaccine availability, infection rates, or other factors that could impact testing and vaccination outcomes over the study. The small number of sites precludes inclusion of a site-level random effect so site will be included as a fixed effect to account for between site differences in participant characteristics and local epidemic trends. The clustered version of the robust (i.e., sandwich) variance estimator will be used in all analyses to ensure correct inference even in the presence of other sources of within-cluster correlation in the data not captured in the model.⁷² For the participant outcomes, the probability of testing and vaccination (binary outcomes) will be modeled using logistic or log binomial regression based on model fit and consistency with model assumptions. The total number of tested/vaccinated network members will be modeled using negative binomial regression with total network size as an offset to account for differences among participants in the number of named network members.⁷³ A second analysis will treat each network member as an observation (tested/vaccinated or not) and will model the likelihood that network members are tested/vaccinated using logistic regression with random effects at the level of the study participant. We will also include a fixed effect for site. This approach will also allow us to examine whether characteristics of the network members (e.g., trust, social influence and social control within a dyad) are associated with probability of testing/vaccination.

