Power Calculations. Statistical power for Aim 1 was computed across a range of plausible effect sizes and outcome prevalence estimates. Power was estimated conservatively, assuming that of the 800 total participants and their network members, 10% would meet the current CDC recommended criteria for testing (recent exposure, symptoms, or congregate housing) and thus the sample size for the primary testing outcome was estimated at N=80 eligible participants. We assumed that 30% would previously have been fully vaccinated or infected with COVID-19 in the past 6 months, resulting in an analytic sample size for vaccination outcomes of N=560 participants and their network members. Power may change depending on the evolution of the pandemic (e.g., changes in infection rates, prevalence of variants, and/or local public health guidance regarding testing and booster vaccine recommendations), and will be higher with broader testing eligibility, higher outcome prevalence, and for analyses treating each network member as a separate observation. For each outcome, we computed minimum detectable effect sizes given estimated rates of testing and vaccination in the control group. We estimated 3-month testing rates among those eligible for testing of 10% in the control group. Based on our ongoing influenza vaccination work, as a starting point for calculations we estimated 3-month vaccination rates among study participants and their network members of approximately 30%. All calculations were conducted in Stata/SE version 15.1 with alpha=0.05, two-sided tests, and a 2:1 ratio of randomization to the intervention vs. control group. For participant testing (primary outcome 1), with a sample size of 80 eligible participants and control group testing prevalence of 10%, we would have 80% power to detect differences of 28 percentage points or more (proportion tested in the intervention group $\geq 38\%$). For participant vaccination (primary outcome 2), with a sample size of 560 and vaccination prevalence of 30% in the control group, we would have 80% power to detect differences of ≥ 12 percentage points (proportion vaccinated in the intervention group $\geq 42\%$). For evaluating interaction effects (Aim 1b), with a sample size of 560 we would have $>80\%$ power to detect an interaction between intervention assignment and an evenly distributed binary covariate (50% in group A and 50% in group B) when vaccination prevalence in the control group is 30% and the intervention increases vaccination to 40% in group A and 69% in group B (e.g., the intervention is more effective in group B). For the participant testing outcome, we will have limited power to detect interaction effects except those of very large magnitude, but will explore differences in testing across

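### Primary testing outcome: with about 8 to 19 events planned, the sandwich-Wald regression is too conservative with arm alone and fragile once site and time enter; a penalised method should be named

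*Combined protocol and SAP*

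**What the plan says.** **Who is analysed.** The Primary Outcomes section restricts the testing analysis: "Only participants reporting symptoms, exposure, and/or congregate housing will be included in the primary testing outcome analysis". The Power Calculations section takes this group as 10% of 800, so that "the sample size for the primary testing outcome was estimated at N=80 eligible participants". It adds: "We estimated 3-month testing rates among those eligible for testing of 10% in the control group". From these inputs it concludes that "we would have 80% power to detect differences of 28 percentage points or more", that is, 10% vs 38%, using "alpha=0.05, two-sided tests, and a 2:1 ratio of randomization to the intervention vs. control group". The Study Design and Randomization sections both give 1:1.

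**How it is analysed.** The Primary and Secondary Outcome Analysis section treats testing and vaccination alike. The initial Aim 1a model contains the arm indicator alone. Participant and network terms then follow as "covariates to improve the precision of the estimates", with their number left open. The section also adds a time-trend term, and "so site will be included as a fixed effect to account for between site differences in participant characteristics and local epidemic trends". Logistic or log-binomial is chosen on model fit, and clustered sandwich variance applies throughout.

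**What is not stated.** The plan does not say whether site and time belong to the initial model, or what the cluster is for a participant-level outcome. It names no small-sample method and no rule for separation or non-convergence. Bayesian methods appear only for interactions and missing data.

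**The concern.** A recipe that suits 560 people with 30% or more vaccinated is carried over unchanged to 80 people with very few events. Maximum likelihood gives an infinite coefficient when an arm or a site has no tested participant. Wald and sandwich inference relies on large-sample behaviour that 8 to 19 events do not supply. Because link, cluster unit, model terms and handling of non-convergence are all open, the analyst would settle them for a primary outcome after seeing the data. At stake are lost power on an outcome that has little to spare, overstated odds ratios in the adjusted models, and avoidable post-hoc choices.

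**Working it through.** **Inputs from the plan.** N=80; control rate 10%; detectable rate 38%; two-sided alpha 0.05; four sites with targets 150/250/250/150 (Table 1). Allocation is 1:1 in the design and 2:1 in the power calculation.

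**Assumptions not in the plan.** Eligible people fall in proportion to the site targets (15/25/25/15). There are no true site, time or covariate effects. Time is linear. The number of covariates is 0 to 8.

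**1. The plan's own figure.** Two-proportion normal approximation with 27 control and 53 intervention:
- pooled rate = (27×0.10 + 53×0.38)/80 = 0.2855
- null SE = √(0.2855×0.7145×(1/27+1/53)) = 0.1068
- alternative SE = √(0.09/27 + 0.2356/53) = 0.0882
- power = Φ((0.28 − 1.96×0.1068)/0.0882) = Φ(0.80) = 79%

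The stated 80% is reproduced. At 40/40 the same formula gives 85%.

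**2. Events.**
- No effect: 80×0.10 = 8
- 10% vs 38% at 1:1: 40×0.10 + 40×0.38 = 4 + 15.2 = 19.2
- 10% vs 38% at 2:1: 27×0.10 + 53×0.38 = about 23

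Arm, three site terms and one time term make 5 parameters: 8/5 = 1.6 to 19.2/5 = 3.8 events per parameter. Four covariates make 9 parameters: 0.9 to 2.1.

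**3. Arm-only model, 40/40, exact enumeration.**
- No finite estimate under no effect: 1 − (1 − 0.9^40)² = 2.9%. At 10% vs 38%: 1.5%.
- Wald test under no effect: rejects 1.2%.
- Example with 8 events split 1 vs 7. Log odds ratio = ln(7/33) − ln(1/39) = 2.113; SE = √(1/7+1/33+1+1/39) = 1.095; z = 1.93, not significant. Pearson on the same table: 0.15/√(0.1×0.9×2/40) = 2.24. A 0 vs 8 split has no Wald statistic. So at the expected null count no split can reach 5% by Wald.
- Firth penalty: in this model it adds 0.5 to each cell. The penalised-likelihood-ratio statistic for 1 vs 7 is 2[1.5 ln(1.5/4.5) + 39.5 ln(39.5/36.5) + 7.5 ln(7.5/4.5) + 33.5 ln(33.5/36.5)] = 4.86, above 3.84.
- Firth over all tables: rejects 4.5% under no effect. Power at 10% vs 25% is 43%, against 37% for Wald.

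**4. Site and time terms.**
- Chance that some site has no tested participant, no effect: 1 − (1−0.9^15)²(1−0.9^25)² = 1 − 0.794²×0.928² = 45.7%.
- At 10% vs 38% (average rate 24%): 1 − (1−0.76^15)²(1−0.76^25)² = 3.4%. Adding 0.9^40 = 1.5% for an empty control arm gives about 5%.
- Simulated full logistic model without a finite solution: about 45-50% under no effect and 5-8% at 10% vs 38%.
- After zero-event sites are dropped, the arm effect is inestimable under no effect in about 3% with no covariates and 18% with four.
- Log-binomial with site and time failed in 51% (no effect) and 18% (10% vs 38%); these rates depend on the fitting algorithm.

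**5. Inference among fitted models (simulation).** The true odds ratio at 10% vs 38% is (0.38/0.62)/(0.10/0.90) = 5.5.

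| Quantity | Result |
|---|---|
| Median odds ratio, site + time, no covariates | about 6.5 |
| Same, 4 covariates | about 7.6 |
| Type I error, participant-level sandwich, 0-4 covariates | about 3-6% |
| Same, 8 covariates | about 8-10% |
| Type I error, sandwich clustered on 4 sites | about 11-15% |

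These carry simulation error of around a percentage point and shift with the handling of zero-event sites.

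**6. The alternative.** Firth logistic regression with arm and site always gave a finite fit in simulation. Its penalised-likelihood-ratio test rejected about 4-5% under no effect, and the median odds ratio at 38% was 5.2 to 5.4. Keeping a sandwich standard error with the Firth estimate gave 10-13% type I error, so the test must change together with the estimator.

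**The case against.** The tempting stronger reading is that a primary result rests on a model that often cannot be estimated and that yields false positives. The documents do not support it.

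- The initial Aim 1a model has arm alone, fails in about 3% of null trials and errs on the conservative side. At 38% its Wald test still has 84% power. This stands.
- The 46% concerns a site coefficient, which is a nuisance parameter. A site with no events carries no information on the arm contrast, and the arm effect usually survives its removal. At the design effect the problem is uncommon. This stands.
- Clear inflation at participant level needs about 8 covariates, and the plan gives examples without a count. This stands. The site-clustered inflation needs no covariates, but it depends on a reading the plan merely leaves open.
- N=80 is described as conservative. At 160 eligible the arm effect was almost always estimable (0-0.1% failures), and sandwich type I error was 4.2-5.8% even with 8 covariates. That eases the concern if eligibility proves broader, but no fallback exists if 80 proves right.
- Much of the power gain comes from leaving the Wald test. Arm-only Pearson or ordinary likelihood-ratio tests reach 44% at 10% vs 25%, but they reject 5.9% and 6.5% under no effect. Firth stays below 5% and also handles empty sites.

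**Conclusion.** The concern holds as a gap in the method for primary outcome 1, at should-fix level. The planned arm-only analysis can nearly always be run but spends only about 1.2% of its 5% alpha, and it gives up about 6 points of power at 10% vs 25% (43 − 37). The adjusted models have no finite full solution in roughly half of null trials and exaggerate the odds ratio at 38%. Their error rate depends on two things the plan does not fix: the number of covariates and the cluster unit.

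The event counts, the arm-only results and the zero-event-site probability are exact, given 80 people, 10% in controls, 1:1 allocation and, for sites, a proportional split. The other figures are simulated under the assumptions listed. The 37% vs 43% comparison is for the arm-only model; the gain with site added rests on simulation and may be smaller. The vaccination outcome is not affected.

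**What to change.** For primary outcome 1 only, state in the SAP:

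1. The primary analysis is Firth-penalised logistic regression with arm and site, site being a stratification factor. It uses a penalised-likelihood-ratio test and profile penalised-likelihood confidence limits in place of the sandwich-Wald test. This also settles which terms the initial model contains and removes the cluster-unit question for this outcome.
2. Time and covariate terms are secondary analyses, fitted by the same penalised method.
3. The planned Bayesian partial pooling stays for exploratory interactions.

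Keep the planned model for vaccination. The cost is one SAP paragraph and a standard software routine. The downside is a slight shrinkage of the estimate toward no effect.

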The scientific premise of C3 is to engage people who have been interacted with law enforcement in COVID-19 prevention (testing and/or vaccination) through social network mobilization combined with theory-driven COVID-19 prevention messaging delivered in an interactive group format. Eligible individuals will be enrolled into C3. Using a two-arm 1:1 randomized controlled trial design, 800 participants will be enrolled into either a: 1) COVID-19 prevention education arm (Education Arm) or, 2) a network mobilization change agent intervention (Motivational Arm); the latter is a Type I network intervention that includes specific training on mobilization of network members which we have adapted to COVID-19 from HIV prevention.^{2,3} Training occurs in a group-based setting of 8-10 enrolled participants facilitated by a community facilitator and Motivational Interviewing trained interventionist. At 30 days, a 15-20-minute phone booster communication session reinforces the intervention content. Information on the personal social network members of these participants will be collected during the study visit (estimated at n~2-4/participant, total~3,200) using a network elicitation and collection approach prior to randomization as in previous work.^{1,2}

Primary outcomes are: 1) the number of study participants who undergo COVID-19 testing (situation appropriate) at 3 months; and 2) the number of study participants who receive at least one COVID-19 vaccine dose at 3 months. Secondary outcomes are the same as primary, except measured among people who are in the networks of primary participants (referred to as secondary subjects moving forward). Additional secondary outcomes include: COVID-19 testing and vaccination knowledge; intent to receive a COVID-19 test or vaccination, and intent to participate in a future vaccine trial. Additional analyses will begin to understand the complex relationships between testing and vaccine statuses and proclivity to test (and potentially obtain a vaccine booster) among both study participants and their network members. For example, do those who are vaccinated serve as more effective change agents? Are vaccinated persons more or less likely to test compared to unvaccinated persons? Are people with prior COVID infection less likely to get vaccinated than those without a known history of infection? We have leveraged the RADx-UP phase I infrastructure to adapt the intervention resulting in C3.

AIMS

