- (4) previous direct or indirect exposure to law enforcement
- (5) has covid vaccination and applicable boosters (self-report, not required to show proof)

Exclusion Criteria:

- (1) inability to provide informed consent; and
- (2) active COVID-19 symptoms per CDC.⁵⁶

(3) Parolees currently living in a court ordered treatment center as part of parole and/or individuals otherwise meeting the definition of a prisoner

We include participants with prior COVID-19 vaccination (completed series) or recent COVID-19 infection in past 3 months given that they may be important change agents. We will remove the estimated numbers (n=160) who are vaccinated/recent infection from our primary analysis if there are no future vaccine boosters or new vaccines required (i.e., new variant). Candidate participants with COVID-19 symptoms will be referred for free testing at existing partners for each of the study sites.

Sex as a Biologic Variable. Both sexes and all genders will be included in this study with exploratory analyses to determine any differences in intervention effects.

STUDY VISIT PROCEDURES

[figure not shown]
Study procedures include:

- 1) Informed consent, locator form
- 2) Baseline survey with network elicitation
- 3) Randomization
- 4) Motivational or Education intervention (approximately 3 hours)
- 5) Booster/Communication 30-day \pm 7 days phone follow-up
- 6) 3-month follow-up phone survey \pm 7 days to assess participant and network COVID-19 testing/vaccination history

Eligible candidate study participants will undergo written informed consent. Following consent, study participants will complete a survey (Baseline Assessment) includes variables of interest and the social network inventory. Randomization will occur following the survey, and participants will be assigned to one of two concurrent Motivational or Educational group-level sessions. Sessions will be held weekly, also with availability, in the evening or on weekends. Study staff will be notified of group allocation and bring study participants to the appropriate group session/intervention rooms.

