Between 8-10 study participants will participate in each intervention room and the interventions (either Motivational or Educational) co-facilitated by both trained research staff and community members. Please note that community members will either be part of an IRB approved study site or will have an Individual Investigator Agreement with approved reliance on the University of Chicago IRB. All study sites have approved COVID-19 infection control plans for research participant studies and guidance updates will be continuously monitored by multi-PI [name]. The entire study visit including group intervention will take 4-5 hours. All participants (irrespective of study arm) will receive referral information for COVID-19 testing/vaccination. The group sessions may be conducted in-person or virtually depending on changes in the COVID-19 response.

Informed Consent: Eligible participants will be asked to participate in written informed consent using either a paper consent or electronic consent. The following consent processes applies to both the study consent form and the release of information form.

In-person Consent Methods:

Paper Consent:

A study team will provide the subject with a copy of the study consent. The consent document will be reviewed and any questions regarding the study will be answered by the study team. If the subject agrees to participate in the study, they will be instructed to sign the consent form. Staff will also sign and the subject will be provided with a final signed copy. A signed copy will be stored by the study team.

Electronic Consent:

Consent may be obtained in-person electronically via RedCAP. Study staff can present the consent to the subject on the tablet or on paper depending upon subject preference. The consent document will be reviewed and any questions regarding the study will be answered by the study team. If the subject agrees to participate in the study, the subject will be instructed to sign the consent form via RedCAP e-consent signature. Staff will also sign the consent form and update the RedCAP link to provide the subject with a final, signed version of the consent form via email. The final signed consent document will be stored in RedCAP.

Remote Consent Methods:

Written consent signature using paper mail:

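### Both arms are delivered in rooms of 8-10, but the clustered sandwich variance names no cluster and the vaccination power includes no design effect

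*Combined protocol and SAP*

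**What the plan says.** All references are to the combined protocol and SAP.

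- **Delivery.** Study Design: "Training occurs in a group-based setting of 8-10 enrolled participants". Study Visit Procedures: "Between 8-10 study participants will participate in each intervention room", for either intervention, and "participants will be assigned to one of two concurrent Motivational or Educational group-level sessions".
- **Allocation.** The Randomization paragraph assigns individual participants 1:1.
- **Staff.** Staff Training and Fidelity gives each arm its own staff. Under the mini-booster section, the person who gave the initial intervention also makes the 30-day call.
- **Analysis.** Primary and Secondary Outcome Analysis provides for "random effects as appropriate to account for clustering of network members within participants", and later for participant-level random effects in the network-member model. On site it says "The small number of sites precludes inclusion of a site-level random effect so site will be included as a fixed effect". It then says "The clustered version of the robust (i.e., sandwich) variance estimator will be used in all analyses", as a safeguard against correlation that the model does not capture. The unit of clustering is not stated. For the first comparison of arms, "The initial analysis will include an indicator for intervention assignment as the only independent variable".
- **Power.** Power Calculations gives 80% power for vaccination at 30% versus 42%, with 560 analysed, two-sided alpha 0.05 and 2:1 allocation. No ICC, room size or design effect appears.

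**The concern.** People who share a room also share facilitators, discussion and group-chosen topics, so their later vaccination decisions may be correlated even though each was randomised separately. A clustered sandwich variance deals with this only if the cluster contains the room-mates. The one cluster the analysis text defines, the participant, does that job for network members. For the participant's own vaccination outcome it reduces to an ordinary robust variance with one observation per cluster. An analyst could follow the text faithfully and still leave room correlation out of the standard error of a primary outcome. If the analyst does cluster on session, the test is better founded but the stated power no longer describes it. The testing primary is little affected: with 80 of 800 expected to be eligible, a room of 9 contributes about 9 × 0.10 = 0.9 analysed people.

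**Working it through.** **Inputs from the documents.** 800 enrolled; 560 in the vaccination analysis; rooms of 8-10 (9 used); 30% versus 42%; two-sided alpha 0.05; 2:1 in Power Calculations, 1:1 in the design. **Assumed:** room ICC of 0.01, 0.02 or 0.05, and the 30% who are removed spread evenly over rooms.

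**Step 1: reproduce the stated power.** Two-proportion formula with pooled null variance:

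power = Φ[(0.12 − 1.96·SE₀)/SE₁]

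At 2:1 the arms are 186.7 (control) and 373.3, and the pooled rate is (0.30 + 2 × 0.42)/3 = 0.38.
- SE₀ = √[0.38 × 0.62 × (1/186.7 + 1/373.3)] = 0.0435
- SE₁ = √[0.21/186.7 + 0.2436/373.3] = 0.0422
- Power = Φ(0.82) = 79.5%

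This matches the stated 80%, so the calculation treats 560 people as independent. At 1:1 (280 per arm) the same formula gives 84.3%.

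**Step 2: design effect.** Analysed people per room: m = 9 × 560/800 = 6.3. DE = 1 + (m − 1) × ICC = 1 + 5.3 × ICC, which is 1.053, 1.106 and 1.265 at the three ICCs.

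**Step 3: type I error if the participant is the cluster.** 2[1 − Φ(1.96/√DE)] = 5.6%, 6.2% and 8.1%. Null simulations of the arm-only comparison (44 concurrent pairs of rooms of 8-10, each person analysed with probability 0.70, event rate 0.30) gave 5.6-5.7%, 6.3-6.8% and 8.2-8.5%.

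**Step 4: power for 30% versus 42% with arm sizes divided by DE.** For example, at 1:1 and ICC 0.02, 280/1.106 = 253.2 per arm, and power is Φ(0.86) = 80.5%.

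| Room ICC | 2:1, N=560 | 1:1, N=560 | Detectable difference, 1:1 |
|---|---|---|---|
| 0 | 79.5% | 84.3% | 11.3 points |
| 0.01 | 77.4% | 82.4% | 11.6 points |
| 0.02 | 75.3% | 80.5% | 11.9 points |
| 0.05 | 69.4% | 75.0% | 12.8 points |

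At 1:1, power reaches 80% at ICC 0.023 for rooms of 9 (0.020 for rooms of 10, 0.026 for rooms of 8). Simulated power with session clustering agreed: 84.2%, 80.5% and 75.2% at ICC 0, 0.02 and 0.05.

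**Step 5: alternative cluster.** Clustering on the concurrent pair of sessions with a t reference gave simulated power of about 82%, 78% and 73% at ICC 0, 0.02 and 0.05 (1:1, N=560). The figures in Step 4 must not be quoted for that test.

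**Step 6: staff.** Teams belong to one arm and may run many sessions, so a team effect crosses sessions and does not cancel between concurrent rooms. With room ICC 0.02, an assumed team ICC of 0.01 and two or three teams per arm per site, simulated type I error was 7.6-8.7% with session clustering and 6.9-7.9% with pair clustering and a t reference. The documents give neither team numbers nor a team ICC, and the result applies only if teams are regarded as a random source of variation.

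**The case against.** The best defence is that this is a gap in wording. The text does not exclude session as the cluster, and about 800/9 ≈ 89 sessions are enough for a sandwich estimator. The ICC is assumed, and at 0.01-0.02 the excess type I error is small. At 1:1 the stated 12 points keep 80% power up to an ICC of about 0.02. The lack of margin at 2:1 comes from an allocation ratio that contradicts the design. The analytic N is also unsettled. The eligibility section says "We will remove the estimated numbers (n=160) who are vaccinated/recent infection from our primary analysis" if no further boosters or new vaccines are required, which leaves 640. There m = 9 × 640/800 = 7.2, and 1:1 power is 84.9% at ICC 0.02 and 79.1% at 0.05. All of this stands and limits the size of the point. It does not supply the missing cluster.

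A reader might infer that the variance is to be clustered on the four sites, which would be far too few. The documents do not support that: the sentence just before makes site a fixed effect because there are so few.

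A reader might also infer that naming the session guarantees a nominal error rate, because anything beyond the room is shared by concurrent sessions and cancels. Shared week and site effects do largely cancel between arms. The arm-specific staffing means that team effects need not.

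**Conclusion.** The point holds, at moderate size. For the vaccination primary, the only cluster the analysis text defines leaves room correlation uncorrected, and the published power assumes independence. Everything beyond the reproduced 79.5% rests on assumed ICCs, rooms of about 9 and even removal of the 30%. Under those assumptions the type I error is a little above nominal at small ICCs and about 8% at 0.05. The power loss at 1:1 is about 2 points at ICC 0.01, 4 at 0.02 and 9 at 0.05.

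It would go too far to conclude that the trial is underpowered or that its primary test is invalid. The documents leave session clustering open, and the 1:1 design has some headroom. The stronger reason to act is that the choice of cluster affects a primary p-value and should not be left until the data have been seen.

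**What to change.** 1. In Primary and Secondary Outcome Analysis, state that for the participant outcomes and the network models the sandwich variance is clustered on the group session to which the participant was assigned. Using assigned session gives non-attenders a cluster, consistent with the commitment under Attrition and missing data to analyse everyone enrolled. Each participant's network members fall within that session, so one definition serves throughout.
2. Record session, concurrent-pair and facilitator-team identifiers at delivery.
3. Add a sensitivity analysis that allows for facilitator team.
4. Restate the vaccination power or detectable difference at 1:1 over an assumed ICC range, using the cluster and reference distribution that the analysis will use. If pairs with a t reference are preferred, use the lower figures in Step 5.

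The cost is a few SAP sentences and three ID variables, with no change to sample size. Intervals become slightly wider and the stated power slightly less favourable. Session clustering is somewhat conservative in the arm-only model if week or site effects are shared: simulated type I error was 2.6-2.9% when an ICC of 0.05 was entirely shared by the pair.
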